13.3. Vital Signs

Vital signs will include pulse rate, systolic and diastolic blood pressure (after the subject has been sitting for at least 5 minutes) and body temperature.

Vital signs will be collected at the Screening visit and at Baseline/Day 1, Week 4, Week 8, Week 12, Week 16, Week 20, Week 24, Early Termination visit, and at Week 32/Follow-up.

Height and weight will be measured at Screening for all subjects. Weight assessments will be conducted at Baseline/Day 1, Week 12, Week 24 and Early Termination.

All vital signs including height and weight (absolute values and change from Baseline) will be summarized as continuous (Baseline and scheduled visits only). Last post-Baseline results (including unscheduled visits in the derivation) will also be included.

The number and percentage of subjects who met criteria of potential CS value ([Section 21.4](#)) for vital signs and weight will be summarized (Baseline and scheduled visits only). Last post-Baseline results (including unscheduled visits in the derivation) will also be included.

Distribution of pulse rate, systolic and diastolic blood pressure will be displayed graphically as boxplot by treatment group for Baseline and each scheduled visit and maximum post-Baseline (including unscheduled visits in the derivation) values.

This document is confidential.

By-subject listing of subjects with potentially CS vital signs and weight will be provided.

All vital signs results will be listed on the Safety population.

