13.6.2. Peak Expiratory Flow

Peak expiratory flow (PEF) testing during the clinical study will be performed under the supervision of qualified study personnel. Peak expiratory flow measurements should consist of 3 good efforts, with the best result documented. Obtained PEF values will be compared to predicted values based on the subject's age, sex and height.

PEF testing will be performed for all subjects at screening, Baseline/Day 1, Week 8, Week 16, Week 24, Early Termination, and Week 32/Follow-up visits. For subjects reporting a medical history of asthma, PEF testing will be performed at all visits during the clinical study. For subjects diagnosed with de novo asthma, PEF testing will be performed at all visits, starting with the visit in which the diagnosis was confirmed.

Following PEF parameters will be summarized as a continuous variable (Baseline and scheduled visits only):

- Actual peak expiratory flow rate
- Predicted peak expiratory flow rate
- Actual PEF of predicted value (%).

These PEF parameters will be summarized separately for the subset of subjects with and without history of asthma.

The number and percentage of subjects with PEF < 80% of predicted value will be summarized by treatment group, visit (baseline and scheduled visits only), and medical history of asthma (with and without history of asthma).

All PEF results will be listed on the Safety population.

This document is confidential.

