13.6.3. Asthma Control Test

Subjects with a medical history of asthma will take an Asthma Control Test (ACT) at Screening, Baseline/Day 1, Week 4, Week 8, Week 12, Week 16, Week 20, Week 24, Early Termination visit, and Week 32/Follow-up. Subjects with de novo asthma will complete the ACT testing beginning from de novo diagnosis and at all subsequent scheduled visits.

The ACT is composed of 5 questions. For each question, the subject will choose the best answer out of 5 possible answers. The test provides a numerical score ranging from 5 to 25 to assess asthma control; a higher score indicates better asthma control while a score of 19 or less indicates the subject's asthma may not be under control.

ACT total score (absolute values and change from Baseline) will be summarized as a continuous variable (Baseline and scheduled visits only).

The number and percentage of subjects with an ACT score ≤ 19 will be summarized (scheduled visits only).

The ACT results and the ACT score will be listed on the Safety population.

This document is confidential.

14. Changes from Analysis Planned in Protocol

In protocol Section 9.10 (Prior and Concomitant Therapy), concomitant medications/therapies are defined as any therapies taken during the study (i.e., from the screening visit to the end of study).

However, for the analysis purpose, concomitant medications/therapies are defined as medications/therapies which start or stop or ongoing on or after the 1st injection of study drug.

In protocol stratification variable weight is named 'body weight at baseline'. This wording is corrected to 'weight at randomization', to clarify that this is the body weight at the time of randomization and how this information is provided by the investigator.

It has been further clarified how to deal with data collected on or after the use of rescue therapy in order to consistently treat subjects as treatment failures across all the analyses. Efficacy data collected on or after the use of rescue therapy will be set to the worst case value for continuous variables and subject's binary response will be calculated based on the underlying continuous values as stated in [Section 8.3](#).

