	14.3.4.1.1.2	Shift from Baseline for Hematology by Reference Ranges	Safety Population
	14.3.4.1.1.3	Summary of Potentially Clinically Significant Hematology	Safety Population
	14.3.4.1.1.4	Listing of Subjects with Abnormal Hematology Results	Safety Population
	14.3.4.1.1.5	Listing of Subjects with Potentially Clinically Significant Hematology Results	Safety Population
14.3.4.1.2		Blood Chemistry Data	
	14.3.4.1.2.1	Summary of Laboratory Data for Clinical Chemistry	Safety Population
	14.3.4.1.2.2	Shift from Baseline for Clinical Chemistry by Reference Range	Safety Population
	14.3.4.1.2.3	Summary of Potentially Clinically Significant Clinical Chemistry	Safety Population
	14.3.4.1.2.4	Listing of Subjects with Abnormal Clinical Chemistry Results	Safety Population
	14.3.4.1.2.5	Listing of Subjects with Potentially Clinically Significant Clinical Chemistry Results	Safety Population
14.3.4.1.3		Urinalysis Data	
	14.3.4.1.3.1	Summary of Laboratory Data for Urinalysis	Safety Population
14.3.4.1.4		Pregnancy Test	
	14.3.4.1.4.1	Summary of Pregnancy Test Results by Visit	Safety Population
14.3.4.2		Vital Signs	
	14.3.4.2.1	Summary of Vital Signs, Height and Weight	Safety Population

This document is confidential.

Header	Table Number	Name	Analysis Set
	14.3.4.2.2	Proportions of Subjects with Potentially Clinically Significant Vital Signs and Weight	Safety Population
	14.3.4.2.3	Listing of Subjects with Potentially Clinically Significant Vital Signs and Weight	Safety Population
14.3.4.3		Electrocardiogram (ECG) Data	
	14.3.4.3.1	Summary of Observed Values and Changes from Baseline for Electrocardiogram (ECG) Parameters by Visit	Safety Population
	14.3.4.3.2	Summary of Electrocardiogram (ECG) Interpretation	Safety Population
	14.3.4.3.3	Summary of Electrocardiogram (ECG) Findings by Visit	Safety Population
14.3.4.4		Other Safety	
	14.3.4.4.1	Summary of Physical Examination	Safety Population
	14.3.4.4.2	Shift from Baseline in Physical Examination	Safety Population
	14.3.4.4.3	Listing of Subjects with Abnormal Results in Physical Examination	Safety Population
	14.3.4.4.4	Summary of Respiratory Assessments – Peak Expiratory Flow (PEF)	Safety Population
	14.3.4.4.5	Summary of Respiratory Assessments – Peak Expiratory Flow (PEF) for Subjects with Asthma History	Safety Population
	14.3.4.4.6	Summary of Respiratory Assessments – Peak Expiratory Flow (PEF) for Subjects without Asthma History	Safety Population

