	14.3.4.4.7	Summary of Peak Expiratory Flow (PEF) < 80% of Predicted Value	Safety Population
	14.3.4.4.8	Summary of Peak Expiratory Flow (PEF) < 80% of Predicted Value for Subjects with Asthma History	Safety Population
	14.3.4.4.9	Summary of Peak Expiratory Flow (PEF) < 80% of Predicted Value for Subjects without Asthma History	Safety Population
	14.3.4.4.10	Summary of Asthma Control Test (ACT)	Safety Population
	14.3.4.4.11	Summary of Asthma Control Test (ACT) Score <= 19	Safety Population
	14.3.4.4.12	Summary of Respiratory Examination	Safety Population

This document is confidential.

19. Index of Figures

This section contains lists of the figures tentatively planned for this study. Changes in the number or content of planned listings are not considered deviations from this SAP.

Figure Number	Name	Analysis Set (Examples)
14.1.1.7	Time (days) to Permanent Discontinuation of Study Drug by Reason for Discontinuation	ITT Population
14.2.1.1.2	Bar Chart of Proportion of Subjects with an Improvement of ≥ 4 from Baseline in Weekly Average PP NRS at Week 16 - Missing as Non-Responder	ITT Population
14.2.1.1.4	Bar Chart of Proportion of Subjects with an Improvement of ≥ 4 from Baseline in Weekly Average PP NRS at Week 16 - Missing as Non-Responder	PP Population
14.2.1.1.6	Sensitivity Analysis of Proportion of Subjects with an Improvement of ≥ 4 from Baseline in Weekly Average PP NRS at Week 16 - Tipping Point Analysis	ITT Population
14.2.1.1.12	Subgroup Analysis of Proportion of Subjects with an Improvement of ≥ 4 from Baseline in Weekly Average PP NRS at Week 16 with Forest Plot - Missing as Non-Responder	ITT Population
14.2.1.2.2	Bar Chart of Proportion of Subjects with an IGA Success at Week 16 - Missing as Non-Responder	ITT Population
14.2.1.2.4	Bar Chart of Proportion of Subjects with an IGA Success at Week 16 - Missing as Non-Responder	PP Population
14.2.1.2.6	Sensitivity Analysis of Proportion of Subjects with an IGA Success at Week 16 - Tipping Point Analysis	ITT Population
14.2.1.2.12	Subgroup Analysis of Proportion of Subjects with an IGA Success at Week 16 with Forest Plot - Missing as Non-Responder	ITT Population
14.2.2.1.2	Bar Chart of Proportion of Subjects with an Improvement of ≥ 4 from Baseline in Weekly Average PP NRS at Week 4 - Missing as Non-Responder	ITT Population
14.2.2.1.4	Bar Chart of Proportion of Subjects with an Improvement of ≥ 4 from Baseline in Weekly Average PP NRS at Week 4 - Missing as Non-Responder	PP Population

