	16.2.8.2.1	Vital Signs, Height and Weight	Safety Population
	16.2.8.2.2	Electrocardiogram (ECG)	Safety Population
	16.2.8.2.3	Physical Examination	Safety Population
	16.2.8.2.4	Respiratory Assessment – Medical Interview	Safety Population
	16.2.8.2.5	Respiratory Assessment – Peak Expiratory Flow (PEF)	Safety Population
	16.2.8.2.6	Known Asthma, Wheeze, Dyspnea and Cough Triggers	Safety Population
	16.2.8.2.7	Asthma Control Test (ACT)	Safety Population
	16.2.8.2.8	Subjects with a drop by >= 15% from Baseline for either PEF or ACT	Safety Population

This document is confidential.

21. Appendices

Efficacy data collected on/after the use of rescue therapy will be set to the worst case value for continuous variables (e.g. weekly averages of PP NRS) and subject's binary response will be calculated based on the underlying continuous data (see [Section 8.3](#)) prior to conducting the MI and Tipping Point analysis.

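### PEF is tabulated only as levels by visit and as the share below 80% of predicted, so no table compares falls from the subject's own baseline between arms

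*SAP*

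**What the plan says.** Section 13.6.2 plans two kinds of PEF table.

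- **Continuous:** "Following PEF parameters will be summarized as a continuous variable (Baseline and scheduled visits only"). The parameters are the actual rate, the predicted rate and "Actual PEF of predicted value" in percent. They are repeated for subjects with and without a history of asthma.
- **Categorical:** "The number and percentage of subjects with PEF < 80% of predicted value will be summarized by treatment group", by visit (baseline included) and by asthma history.

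The Index of Tables (Section 18) agrees. Tables 14.3.4.4.4 to 14.3.4.4.6 are titled "Summary of Respiratory Assessments – Peak Expiratory Flow (PEF"), overall and by asthma history. Tables 14.3.4.4.7 to 14.3.4.4.9 are titled "Summary of Peak Expiratory Flow (PEF) < 80% of Predicted Value", with the same split. No PEF table of change, shift or falls is indexed.

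The one PEF output that uses baseline is Listing 16.2.8.2.8 in the Index of Listings (Section 20): "Subjects with a drop by >= 15% from Baseline for either PEF or ACT". Section 13.6.2 does not mention it, and Section 20 calls its listings tentative.

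The wording for other measures differs. Section 13.3 has "All vital signs including height and weight (absolute values and change from Baseline) will be summarized as continuous", and Section 13.6.3 has "ACT total score (absolute values and change from Baseline) will be summarized as a continuous variable". Sections 13.2.1 and 13.4 plan the same for laboratory data and ECG.

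**The concern.** New or worsening asthma is an adverse event of special interest (Section 13.1), and asthma-related events go to an independent adjudication committee (Section 2.2). PEF is the objective airway measurement that the SAP collects in this area, and testing is planned for every subject at baseline. The natural use of that baseline is to ask how far each subject has fallen from it, and whether falls are more frequent on nemolizumab than on placebo. The planned tables do not answer this.

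The 80% cut-off has no baseline condition. It counts a subject who was already low and has not changed. It misses a subject who started high and fell a long way without crossing the line. The potentially clinically significant criteria in Section 21.4 avoid both problems for laboratory values and vital signs, because they depend on the baseline value or on a change from it.

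At stake is the between-arm comparison of one objective safety measure. No hypothesis test is involved.

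**Working it through.** **1. Planned tables, measure by measure**

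| Measure | Section | Change from baseline tabulated | Categorical criterion or shift uses baseline |
|---|---|---|---|
| Hematology, chemistry | 13.2.1, 21.4 | yes | yes (shift tables; criteria conditional on baseline value) |
| Vital signs | 13.3, 21.4 | yes | yes (criteria require a change from baseline) |
| ECG | 13.4 | yes | no such criterion stated |
| Physical examination | 13.5 | not applicable | yes (shift from baseline) |
| ACT | 13.6.3 | yes | no (score of 19 or less) |
| PEF | 13.6.2 | **no** | **no** (< 80% of predicted) |

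PEF is the only numerical measure in this comparison with neither. The SAP gives no reason.

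**2. What the 80% cut-off misses**

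Inputs: the cut-off of 80% of predicted (Section 13.6.2) and the drop of 15% (title of Listing 16.2.8.2.8). Assumptions: the predicted value stays the same during the study, and the 15% is relative to the subject's baseline PEF. The listing title does not define it further.

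A subject with baseline b (% of predicted) who loses a fraction f ends at b × (1 − f). The subject is counted only if b × (1 − f) < 80, that is, if b < 80/(1 − f).

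- At f = 0.15: 80/0.85 = 94.1. To one decimal, 94.1 × 0.85 = 79.99 is counted and 94.2 × 0.85 = 80.07 is not. A subject at or above about 94.2% can meet the 15% criterion and stay out of the < 80% table.
- At f = 0.25: 80/0.75 = 106.7. A subject starting at 110% falls to 110 × 0.75 = 82.5% and is not counted.

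**3. What the 80% cut-off counts without any change**

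A subject stable at 78% of predicted is counted at baseline and at every later visit with a test. The baseline row shows how many subjects started low in each arm. It does not show which of the later low values are the same subjects.

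**4. Comparing visit rows is not always like with like**

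Under Section 13.6.2, all subjects are tested at baseline and Weeks 8, 16 and 24. At Weeks 4, 12 and 20, scheduled testing covers only subjects with a history of asthma or de novo asthma. In the overall tables and those for subjects without asthma history, these rows describe a selected group that differs from the baseline row. Paired change from baseline removes that mismatch.

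**5. Whether another PEF output fills the gap**

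Listing 16.2.8.2.8 identifies subjects with a drop but gives no counts by arm. Listing 16.2.8.2.5 shows all PEF data by subject. Neither is a between-arm summary.

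**The case against.** The strongest reply is that airway safety does not depend on PEF alone. Asthma AESIs, adjudicated events, and asthma events with the adjudication outcome are tabulated (Section 13.1). So is the respiratory interview on new or worsening asthma, wheeze, dyspnea and cough (Section 13.6.1), and so is ACT change. Section 13 states that safety summaries are given for each treatment group. All of this stands. A reader might infer that subjects who deteriorate on drug would appear in no between-arm comparison, or that the airway conclusion rests on PEF. The documents support neither inference. The gap is a PEF fall that comes with no reported symptom, diagnosis or adverse event.

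The existing tables also do more than report raw values. Percent of predicted adjusts for age, sex and height, although not for the subject's own baseline. The < 80% table shows the baseline visit and splits by asthma history. Randomization should spread pre-existing low values over both arms. Section 8.1 requires the first quartile and minimum, so the lower tail is visible by visit. Even so, none of this follows the same subject from baseline.

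Finally, counts by arm could be worked out by hand from the listings. That is true, but such counts are not a planned summary, and Section 20 allows listings to change without this being a deviation.

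One might also want the ACT count of 19 or less restricted to subjects above 19 at baseline. That is not supported. Subjects with de novo asthma start the ACT only at diagnosis (Section 13.6.3), so the restriction would drop them, and ACT change is already tabulated.

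**Conclusion.** The point holds as an incomplete descriptive safety summary. No PEF table uses the subject's own baseline, out of line with the SAP's practice for comparable measures. New and pre-existing values below 80% cannot be told apart. The SAP's own 15% drop criterion has no count by arm.

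The size can be stated only as a threshold: at or above about 94.2% of predicted at baseline, a 15% loss goes uncounted in the < 80% tables. This rests on a constant predicted value and a relative reading of the 15%. How many subjects are in that position cannot be said, because the SAP gives no baseline PEF distribution. Any percentage would come from an assumed one and would show who could fall unseen, not who would.

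Nothing here contradicts another part of the SAP, and efficacy conclusions and type I error are untouched. The change is still worth making before unblinding, because it concerns a risk that the SAP singles out and uses data already planned.

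**What to change.** In Section 13.6.2 and the Index of Tables:

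1. Add change and percent change from baseline in actual PEF, and change in percent of predicted, to Tables 14.3.4.4.4 to 14.3.4.4.6.
2. Keep Tables 14.3.4.4.7 to 14.3.4.4.9 as they are and add a baseline-by-post-baseline shift table (< 80% / >= 80% of predicted) beside them. Replacing them with counts among subjects at or above 80% at baseline would remove subjects with low baseline PEF from view.
3. Tabulate, by arm and asthma history, the number and percentage of subjects with a PEF drop of >= 15% from baseline, using the criterion of Listing 16.2.8.2.8. Describe that criterion in Section 13.6.2 and state whether the 15% is relative to baseline PEF.

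No new data, threshold or clinical rule is needed. The cost is SAP wording, a few extra table rows and their programming. The SAP does not show that the 15% flag has already been programmed, so it should not be assumed.

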13.6.3. Asthma Control Test

Subjects with a medical history of asthma will take an Asthma Control Test (ACT) at Screening, Baseline/Day 1, Week 4, Week 8, Week 12, Week 16, Week 20, Week 24, Early Termination visit, and Week 32/Follow-up. Subjects with de novo asthma will complete the ACT testing beginning from de novo diagnosis and at all subsequent scheduled visits.

The ACT is composed of 5 questions. For each question, the subject will choose the best answer out of 5 possible answers. The test provides a numerical score ranging from 5 to 25 to assess asthma control; a higher score indicates better asthma control while a score of 19 or less indicates the subject's asthma may not be under control.

ACT total score (absolute values and change from Baseline) will be summarized as a continuous variable (Baseline and scheduled visits only).

The number and percentage of subjects with an ACT score ≤ 19 will be summarized (scheduled visits only).

The ACT results and the ACT score will be listed on the Safety population.

This document is confidential.

14. Changes from Analysis Planned in Protocol

In protocol Section 9.10 (Prior and Concomitant Therapy), concomitant medications/therapies are defined as any therapies taken during the study (i.e., from the screening visit to the end of study).

However, for the analysis purpose, concomitant medications/therapies are defined as medications/therapies which start or stop or ongoing on or after the 1st injection of study drug.

In protocol stratification variable weight is named 'body weight at baseline'. This wording is corrected to 'weight at randomization', to clarify that this is the body weight at the time of randomization and how this information is provided by the investigator.

It has been further clarified how to deal with data collected on or after the use of rescue therapy in order to consistently treat subjects as treatment failures across all the analyses. Efficacy data collected on or after the use of rescue therapy will be set to the worst case value for continuous variables and subject's binary response will be calculated based on the underlying continuous values as stated in [Section 8.3](#).

It has been further clarified for the definition of weekly diary data: if the intake date of rescue therapy is before and on the last day of the weekly visit window, this week will be treated as treatment failure except for OC analysis and the weekly average will be imputed using the worst case value, refer to [Section 8.3](#).

Additional secondary endpoints were added:

- 1) Proportion of subjects with IGA <= 2 (Responder) will be presented using missing as non-responder for ITT population up to Week 24
- 2) Proportion of subjects with number of pruriginous lesions (PAS item 2) < 20 (Responder) will be presented using missing as non-responder for ITT population up to Week 24.
- 3) PN associated pain frequency rating = 5 (every day, non-responder) will be presented using missing as non-responder for ITT population up to Week 24.
- 4) Change and percentage from Baseline in PN associated pain intensity will be presented using MMRM model for ITT population up to Week 24.

This document is confidential.

15. Reference List

This document is confidential.

16. Programming Considerations

All TFLs and statistical analyses will be generated using SAS® 9.4 or higher (SAS® Institute Inc., Cary, NC, USA) on a SAS Server. Changes to the software version (e.g. upgrades), or use of additional software consistent with the SAP will not be considered a violation of the SAP.

16.1. General Considerations

All TFLs will be produced in accordance to Syneos Health QC Processes (see [Section 17](#)).

- A separate SAS program will be created for each output.
- Each output will be stored in a separate file.
- Output files will be provided in separate Word rtf and as combined PDF format including all outputs in one PDF file.
- Numbering of TFLs will follow International Conference on Harmonization (ICH) E3 Guidance.

16.2. Table, Figure, and Listing Format

16.2.1. General

- All TFLs will be produced in landscape format, unless otherwise specified.
- All TFLs will be produced on paper size A4 using the Courier New font, size 8.
- The data displays for all TFLs will have a 1 inch binding margin on top and bottom of a landscape oriented page and a minimum 1.25 inch margin on the left side and a minimum of 0.75 inch right side.
- Headers and footers for figures will be in Courier New font, size 8.
- Legends will be used for all figures with more than 1 variable, group, or item displayed.
- TFLs will be in black and white (no color), unless otherwise specified.
- Specialized text styles, such as bolding, italics, borders, shading, and superscripted and subscripted text, will not be used in the TFLs, unless otherwise specified. On some occasions, superscripts 1, 2, or 3 may be used (see below).
- Only standard keyboard characters will be used in the TFLs. Special characters, such as non-printable control characters, printer-specific, or font-specific characters, will not be used. Hexadecimal-derived characters will be used, where possible, if they are appropriate to help display math symbols (e.g., μ). Certain subscripts and superscripts (e.g., cm², C_{max}) will be employed on a case-by-case basis.
- Mixed case will be used for all titles, footnotes, column headers, and programmer-supplied formats, as appropriate.

This document is confidential.

